2.5.4 Unscheduled visits

Unscheduled visit measurements of laboratory data, vital signs, and ECG will be used for computation of baseline and worst values and/or grades.

2.5.5 Pooling of centers for statistical analyses

Data from all sites will be pooled together for analyses.

2.5.6 Statistical technical issues

Not applicable.

3 INTERIM ANALYSIS

In order to support project strategic planning, an interim analysis may be conducted after the first 20 patients in each arm evaluable for the primary endpoint. The analysis will have no impact on the trial itself.

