9.5 INTERIM ANALYSES

There are no interim analyses planned for this study.

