Assuming Ki67 value follows a log-normal distribution, $\log(Ki67_{post})$ and $\log(Ki67_{pre})$ will be used to denote the logs of the post-treatment and baseline values respectively. 0.1% will be added to untransformed Ki67 with 0 value to avoid the mathematical anomaly that arises because the log of zero is minus infinity. As a consequence of the assumption of a lognormal distribution, the log proportional changes ie, $\log(Ki67_{post}/Ki67_{pre})$ is also normally distributed. The log proportional change will be compared between treatment arms using an analysis of covariance (ANCOVA) model adjusting for the log Ki67 at baseline. Geometric LS-means ratio of proportional change (and associated 95% CI) between treatment arms will be calculated from the estimate (and associated 95% CI) of the difference of least squared (LS)-means of the log-proportional change (and associated 95% CI) from the ANCOVA model and converted by antilog transformations. For each treatment arm, geometric LS-means of the proportional change from baseline (and associated 95% CI) will be obtained from the ANCOVA model after conversion by antilog transformations. Geometric LS-means of percentage reduction in Ki67 (and associated 95% confidence intervals) will be calculated with 1 minus geometric LS-means of proportional change (and associated 95% confidence intervals). Hypothesis test will not be performed due to early enrollment termination.

Details of primary analysis can be found in [Appendix D](#).

Evaluation of inter-reader variability

The reproducibility of Ki67 measurements among readers will be estimated by calculating an intraclass correlation coefficient (ICC). The definition along with the statistical model for ICC estimation are provided in [Table 3](#).

Table 3 - Estimation of ICC during the trial

Notation	Definition	Model	Consistency or absolute agreement
ICC	The inter-reader agreement on log proportional change from baseline in Ki67 measurement after 14-day treatment period.	Mixed-effect model adjusted for baseline covariate, based on single rating	Absolute agreement

Mean estimations along with 95% confidence intervals will be reported for the ICC. Details of ICC estimation can be found in [Appendix E](#).

The ICC estimate will be checked at the following time-points:

- The interim analysis when 20 patients in each arm evaluable for the primary endpoint ([Section 3](#))

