- The analysis when at least 75% patients of the study completed treatment and Ki67 value available for analysis.
- The analysis when all of the patients completed treatment and Ki67 value available for analysis.

The ICC has a range of 0-1, with 1 denoting highest agreement. The ICC estimate at each analysis will be reviewed with study team, and in case a high inter-reader variability is suspected (eg, ICC <0.8), team would evaluate the necessity of inviting a third adjudicator to provide a single Ki67 result based on the readings of two assessors.

In any case, the decision as to whether adjudication will take place needs to be finalized before database lock.

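### The SAP permits an interim analysis that the protocol does not plan, and calls it free of impact although it is the first checkpoint for a discretionary change to the Ki67 value in the primary analysis

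*SAP*

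**What the plan says.** **Protocol.** Section 9.5 states: "There are no interim analyses planned for this study". The synopsis says there is no data monitoring committee, and 10.1.5 says there are no study committees. Under 6.3 the trial is open-label, and only the central Ki67 assessors are blinded.

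**SAP section 3.** The section provides that "an interim analysis may be conducted after the first 20 patients in each arm evaluable for the primary endpoint"; the purpose given is strategic planning for the project. On consequences it says: "The analysis will have no impact on the trial itself". It does not give the content of the analysis, whether results are split by arm, or who receives them. SAP 2.2 carries a disposition category reserved for an interim analysis, so section 3 is not an isolated line.

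**SAP 2.4.5.1.1.** The ICC is to be checked three times. The first check is "The interim analysis when 20 patients in each arm evaluable for the primary endpoint", with a cross-reference to section 3. The second comes when at least 75% of patients have finished treatment and have Ki67 values, and the third when all have. The trigger reads "in case a high inter-reader variability is suspected (eg, ICC <0.8", after which the "team would evaluate the necessity of inviting a third adjudicator to provide a single Ki67 result based on the readings of two assessors". The only time limit is that "the decision as to whether adjudication will take place needs to be finalized before database lock".

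**SAP 2.1.3.1.** By default the Ki67 value is the geometric mean of the two readers' values. The section says an adjudicator may be used if agreement misses criteria set in advance, and points to 2.4.5.1.1 for them.

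**The concern.** There are two inconsistencies. The protocol plans no interim and the SAP permits one. The SAP also describes that interim as having no effect, while using it as a decision point for how the primary endpoint is measured.

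What is at stake is pre-specification of the endpoint. Blinding protects each individual reading. It does not protect the later choice, made by the study team, between the two-reader value and the adjudicated value. If that team has seen Ki67 by arm, the choice can depend on the result, whether or not anyone intends it. The by-arm geometric mean reductions and the ratios to letrozole are the trial's main output, so a result-dependent choice would bear directly on them.

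**Working it through.** No figure in the plan is wrong on this point, so the check is mainly a comparison of passages.

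1. **Design figures.** The log difference is log(0.15) − log(0.30) = −0.693, with SD 1 and 40 evaluable per arm. Simulating the Hochberg procedure with two-sample t-tests and a shared control (400,000 runs) gives 84.8% marginal and 91.6% disjunctive power. SAP 1.3 states 85% and 91.5%, so the design reproduces.

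2. **Size of the look.** 20 × 3 = 60 evaluable patients at the interim, against 40 × 3 = 120 planned. 60/120 = 50% of the planned information. Enrolment stopped early, so the interim would be a larger share of the patients actually available, if it was reached at all.

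3. **Is the interim acknowledged as a departure?** SAP 1.5 lists only the move from t-test to ANCOVA. SAP 1.6 lists the changes made in SAP version 2, and none concerns the interim. An interim already present in version 1 would not belong in that table, but then no part of the SAP reconciles it with protocol 9.5.

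4. **Can the interim affect the primary analysis?** The route in the SAP is: interim → ICC estimate → review with the study team → possible adjudicator → a different single Ki67 result. By default, Ki67 = exp{[log(reader 1) + log(reader 2)]/2}. The analysed outcome is Y = log(Ki67 post / Ki67 pre) (SAP Appendix D). If adjudication changes Y for patient i by D_i, the unadjusted difference between arms moves by mean(D) in the amcenestrant arm minus mean(D) in the letrozole arm. So the interim can lead to a change in the primary result.

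5. **When would this bias the result?** Adjudication by a blinded reader is not a bias in itself. The problem arises if it is invoked more readily when the two-reader comparison looks unfavourable. Unfavourable results would then be replaced and favourable ones kept.

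6. **Is the rule fixed in advance?** SAP 2.1.3.1 promises criteria. SAP 2.4.5.1.1 supplies an example threshold, a suspicion of high variability, and a team evaluation. It does not say which readings would go to the adjudicator.

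7. **Does the ICC need treatment codes?** Appendix E models the log change with a patient effect, log baseline and residual error, and ICC = σ1/(σ1 + σ2). There is no treatment term. The check can therefore be run on pooled data without codes, and needs no interim by arm.

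**The case against.** The sponsor has several fair replies.

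- **No test remains.** SAP 2.4 and 2.4.5.1.1 remove the hypothesis test and make the confidence intervals descriptive. This stands in full. A reader might infer an inflated type I error, from an extra look or from picking the better of two results. The documents support neither: no error rate is in force, and the SAP offers a decision whether to adjudicate, not a choice between two completed analyses.
- **The ICC is not an arm comparison.** This also stands. The risk comes from whatever else the interim contains, not from the ICC.
- **A by-arm look is inferred.** Correct. A reader might conclude that the team saw Ki67 by arm before settling the endpoint. The documents do not say so, and do not say that the interim took place. Its planning purpose makes a by-arm look plausible, and nothing excludes one.
- **Two later ICC checks can also lead to adjudication.** True, so deleting section 3 alone would not close the route. The rule itself must be fixed.
- **The decision is closed before lock.** That is a safeguard against choosing after the final analysis. It does not cover results seen earlier.
- **A switch would be visible.** SAP 2.4.5.1.3 repeats the analysis for each reader, and 2.4.5.3 repeats it on digital Ki67. This is a real mitigation, but it exposes a shifted headline estimate without correcting it.
- **No impact may mean no effect on enrolment, design or stopping.** That is a possible reading, but the sentence carries no such limit.

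**Conclusion.** The point holds as one of consistency and pre-specification. Protocol 9.5 and SAP section 3 conflict, although the protocol says only that no interim is planned, which is weaker than a prohibition. The no-impact sentence does not fit the SAP's own use of the interim in 2.4.5.1.1. The adjudication rule is discretionary at a stage when arm-level Ki67 might be known.

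The consequence is possible bias in the by-arm estimates and their confidence intervals. Its size cannot be derived: it depends on whether the interim was run, what it showed and to whom, and how far adjudicated values differ from the two-reader values. None of this is in the documents.

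Timing matters for interpretation, because SAP version 2 also records the enrolment stop and a clarification of how the two readings are averaged. The SAP's stated reason for that clarification is consistency with the ICC calculation, and nothing in the documents suggests it followed a look at the data. A dated statement would settle the question. With no test in force, blinded readers and reader-level sensitivity analyses, this is something the sponsor should correct, not a flaw that invalidates the analysis.

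**What to change.** 1. Reconcile SAP section 3 with protocol 9.5. Delete the interim, with its disposition line in SAP 2.2. If it was run, record it as a departure from the protocol, giving its date, its content, who saw it, and whether it came before the enrolment stop and SAP version 2.
2. Correct the no-impact sentence.
3. Keep all ICC checks as stand-alone checks on pooled data with treatment codes removed. The Appendix E model needs no change.
4. Replace the example threshold in 2.4.5.1.1 with a fixed one, and state which readings go to the adjudicator.
5. Finalise the adjudication decision before any Ki67 output by arm is produced, instead of merely before database lock.

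**Cost.** SAP wording only. The sponsor gives up an early by-arm look, which its protocol did not plan, and some discretion over when to adjudicate.

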4 DATABASE LOCK

The final database lock is planned 4 weeks after last patient last visit in the study.

5 SOFTWARE DOCUMENTATION

All summaries and statistical analyses will be generated using SAS version 9.4 or higher.

Appendix A TNM anatomic stage groups

When T is	And N is	And M is	Then the stage group is
Tis	N0	M0	0
T1	N0	M0	1A
T0	N1mi	M0	1B
11	N1mi	M0	1B
T0	N1	M0	IIA
T1	N1	M0	IIA
T2	N0	M0	IIA
T2	N1	M0	IIB
T3	N0	M0	IIB
T1	N2	M0	IIIA
T2	N2	M0	IIIA
T3	N1	M0	IIIA
T3	N2	M0	IIIA
T4	N0	M0	IIIB
T4	N1	M0	IIIB
T4	N2	M0	IIIB
Any T	N3	M0	IIIC
Any T	Any N	M1	IV

Source: Giuliano AE, et al. Breast Cancer-Major changes in the American Joint Committee on Cancer eighth edition cancer staging manual. CA Cancer J. Clin. 2017;67:290–303. doi: 10.3322/caac.21393

Note to programmer:

T0 corresponds to “No evidence of primary tumor” as collected in CRF

N0 corresponds to “No regional lymph nodes metastasis” as collected in CRF.

M0 corresponds to “No distant metastasis” as collected in CRF.

If any of the following is checked, then the stage would be “Not evaluable”.

- Primary tumor cannot be evaluated
- No regional lymph node metastasis
- No distant metastasis.

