5.1 INCLUSION CRITERIA

Participants are eligible to be included in the study only if all of the following criteria apply (in case bilateral breast cancer is diagnosed at the same time, only one location as per Investigator judgment will be selected for all selection and assessment criteria):

Age

- I 01. Participant must be older than 18 years of age inclusive, or country's legal age of majority if the legal adult age is >18 years old at the time of signing the informed consent

Type of participant and disease characteristics

- I 02. Patients with histological or cytological proven diagnosis of invasive breast adenocarcinoma
- I 03. Localized breast cancer eligible for upfront breast conservative surgery or upfront mastectomy: Stage I, Stage II or operable Stage III (excludes T4) (*AJCC Cancer Staging Manual 8th edition 2017*; [15])
- I 04. Participants must be postmenopausal women as defined by one of the following:
- With spontaneous cessation of menses >12 months prior to randomization.
 - Or who have received hormonal replacement therapy but have discontinued this treatment AND have FSH level in the postmenopausal range according to institutional standards (or >34.4 IU/L if institutional range is not available) prior to randomization. (Note: serial FSH measurements are required to confirm postmenopausal status in participants who are not using hormonal replacement therapy and in the absence of amenorrhea >12 months.)
 - Or with status post bilateral surgical oophorectomy.
 - Or post bilateral ovarian ablation through pelvic radiotherapy.
- I 05. A breast tumor size of at least 10 mm in greatest dimension measured by ultrasound
- I 06. Primary tumor must be positive:
- ER ($\geq 1\%$ tumor cell staining by IHC)
 - HER2 non-overexpressing by IHC (0, 1+) or in situ hybridization-negative based on single-probe average HER2 copy number <4.0 signals/cell or dual-probe HER2/centromeric probe for chromosome 17 (CEP17) ratio <2 with an average HER2 copy number <4.0 signals/cell (as per the American Society of Clinical Oncology guidelines).

I 07. Ki67 level of at least 15% at diagnosis from immunohistochemistry of the tumor based on local laboratory results

I 08. ECOG performance status 0-1

Weight

I 09. Not Applicable

Sex

I 10. Female

Informed Consent

I 11. Capable of giving signed informed consent which includes compliance with the requirements and restrictions listed in the informed consent form (ICF) and in this protocol.

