5.2 EXCLUSION CRITERIA

Participants are excluded from the study if any of the following criteria apply:

Medical conditions

E 01. Medical history or ongoing gastrointestinal disorders potentially affecting the absorption of amcenestant or letrozole. Participants unable to swallow normally and to take capsules or tablets. Predictable poor compliance to oral treatment. Participants with known active hepatitis A (positive HA antigen or positive IgM); B (either positive HBs antigen or positive hepatitis B viral DNA test above the lower limit of detection of the assay); C (positive hepatitis C antibody result or quantitative hepatitis C (HCV) ribonucleic acid (RNA) results greater than the lower limits of detection of the assay) infection; or hepatic cirrhosis.

E 02. Participant with any other cancer. Adequately treated basal cell or squamous cell skin cancer or in situ cervical cancer or any other cancer from which the participant has been disease free for >3 years are allowed.

E 03. Evidence of metastatic spread by standard assessment according to local practice.

Prior/concomitant therapy

E 04. Treatment with strong CYP3A inducers within 2 weeks before first study treatment administration or 5 elimination half-lives whichever is longest and cannot be replaced.

E 05. Deleted in Protocol Amendment 02.

- E 06. Treatment with drugs that are sensitive substrates of P-glycoprotein (P-gp) (dabigatran, digoxin, fexofenadine) or of breast cancer resistance protein (BCRP) (rosuvastatin, sulfasalazine) within 2 weeks before first study treatment administration or 5 elimination half-lives whichever is longer.
- E 07. Use of any investigational agent within 4 weeks prior to randomization.
- E 08. Recent use of hormone replacement therapy (last dose ≤ 30 days prior to randomization).
- E 09. Prior anti-cancer treatment is not allowed unless it was completed at least 1 year prior to inclusion into this trial.

Prior/concurrent clinical study experience

- E 10. Previous systemic or local treatment for the new primary breast cancer currently under investigation (including surgery, radiotherapy, cytotoxic and endocrine treatments).

Diagnostic assessments

- E 11. Inadequate hematological function including neutrophils $< 1.5 \times 10^9/L$; platelet count $< 100 \times 10^9/L$, hemoglobin < 8.0 g/dL.

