2 STATISTICAL AND ANALYTICAL PROCEDURES

2.1 ANALYSIS ENDPOINTS

2.1.1 Demographic and baseline characteristics

The baseline value is defined as the last value or measurement taken up to the date and time of the first dose of study treatment irrespective of the treatment. This definition applies for all variables unless otherwise specified.

All baseline safety and efficacy parameters (apart from those listed below) are presented along with summary statistics in the safety and efficacy sections ([Section 2.4.6](#) and [Section 2.4.5](#)).

Demographic characteristics

Demographic variables include race (White, Black or African American, Asian, American Indian/Alaska Native, Native Hawaiian/Other Pacific Islander, Not reported, Unknown), ethnicity (Hispanic or Latino, Not Hispanic or Latino, Not reported, Unknown), age in years (quantitative and qualitative variable: [18-64], [65-84], and ≥ 85 years, height, weight (kg) and ECOG performance status (PS) at baseline.

Medical or surgical history

Medical or surgical history includes relevant history of previous or associated pathologies other than the tumor.

This information will be coded using the version of Medical Dictionary for Regulatory Activities (MedDRA) currently in effect at Sanofi at the time of database lock.

Disease characteristics at diagnosis

The following disease characteristics at initial diagnosis will be described:

- Time from initial diagnosis of breast cancer to first study treatment administration (in weeks),
- Histology
- Disease Location
- Laterality
- Histopathology type
- Stage of the disease. Stage I-IV for breast cancer will be derived from TNM information as collected in CRF based on the rules defined in [Appendix A](#)
- HER2 status
- ER status (local assessment as collected in CRF)
- PgR status (local assessment as collected in CRF)
- Ki67 level (%) (local assessment as collected in CRF, quantitative and qualitative variable: $<15\%$, $\geq 15\%$ to $<20\%$, and $\geq 20\%$)

Disease characteristics at baseline (central assessment)

- Ki67 level (%) (quantitative and qualitative variable: <15%, ≥15% to <20%, and ≥20%)
- ER status
- PgR status
- BCL2 status
- Cyclin D1 status

Prior anti-cancer therapies

- Prior anti-cancer treatment or radiotherapy

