2.4.5.1.2 Subgroup analyses

Evaluation of consistency

The consistency of the results from the primary analysis will be evaluated across pre-defined subgroups in patients available in the subgroup of consideration. The subgroups included but not limited are defined in [Table 4](#). Depending upon the study results, additional subgroups may be examined, and subgroups with small sample sizes may be pooled to create a larger meaningful subgroup. For each subgroup, geometric LS-mean of percentage reduction in Ki67 with their associated 95% CIs and geometric LS-mean ratio of proportional change between treatment arms with their associated 95% CIs will be provided for each treatment arm.

Evaluation of interactions

For each pre-defined factor defined in [Table 4](#), log-fold change in Ki67 will be analyzed using linear regression model with terms for the factor, treatment and their interaction, adjusted by log baseline Ki67. The p-value of the test of interaction will be provided.

Other prognostic factors

Since the results from the primary analysis could be impacted by confounding factors, any potential issues will be examined and, if confirmed, exploratory analysis of the primary endpoint will be done accordingly. A multiple linear regression model will be used to identify prognostic factors among the demographic and baseline characteristics factors described in the [Table 4](#) using a stepwise selection procedure with a 15% significance level for removing effects. For significant prognostic factors identified in the multivariate model, the balance between treatment groups will be assessed.

Table 4 - Subgroup analyses

Prognostic factor	Description
Age	<65 years or ≥65 years
Race	Asian or White or Other
Tumor stage	1 or 2 or ≥ 3
Tumor size (greatest dimension)	≥10 mm to < 20mm, ≥ 20mm
Ki67 level at baseline (per central assessment)	<20% or ≥20%
ER H-score at baseline	Low ER+. (H-score 1-100) or moderate ER+ (H-score 101-200) or high ER+ (H-score 201-300).
Progesterone receptor	< 20% vs ≥20%

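### Three SAP derivation rules fail as written (disease stage, the PEPI ER item and the Day 15 PK window); the primary Ki67 analysis is not affected

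*SAP*

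**What the plan says.** **Stage.** SAP 2.1.1 states that "Stage I-IV for breast cancer will be derived from TNM information as collected in CRF", using the rules in Appendix A. The Appendix A table has 18 T/N/M rows, 17 of them M0. The note below it maps the CRF box for no regional nodal metastasis to N0 and the box for no distant metastasis to M0. It continues "If any of the following is checked, then the stage would be" not evaluable, and lists three boxes: primary tumor not assessable, no nodal metastasis, and no distant metastasis. The last two are the boxes just defined as N0 and M0.

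SAP Table 4 has tumor stage (1, 2, or 3 and above) as one of seven factors. SAP 2.4.5.1.2 tests each factor "using linear regression model with terms for the factor, treatment and their interaction", and adds: "A multiple linear regression model will be used to identify prognostic factors among the demographic and baseline characteristics factors described in the" table. SAP 2.4.5.2 runs a stepwise logistic model on the same factors for the 50% Ki67 decrease.

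**PEPI.** Protocol 8.1.3 and Table 16 score ER status on the Allred score: 0-2 gives 3 points and 3-8 gives 0. SAP Appendix C has the same bands and points but labels the item as H-score. SAP Table 4 runs the H-score up to 300.

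**PK.** SAP 2.4.7.1 admits a concentration to the descriptive statistics only if it was sampled in a listed window. The windows are within 2 h before dosing (Day 7, Day 14) and 2-4 h for 3 h post-dose samples, where the text names Day 14 and Day 15. The protocol Schedule of Activities places the Day 15 sample 24 h after the Day 14 dose, and SAP 2.1.5 ties sampling to that schedule.

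**The concern.** Each rule is an instruction to a programmer, and each gives an empty or undefined result for the ordinary participant if followed literally.

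- **Stage.** The baseline summary would show no stage for any eligible participant. Protocol 6.3 describes no stratification and enrollment stopped early, so this summary is where a reader would check stage balance across small arms. If Table 4 uses the same derivation, the stage subgroup rows and the stage interaction test have no usable levels, and both stepwise models are affected.
- **PEPI.** The ER item has no points for most of the H-score scale, so the total and the risk category (0, 1-3, 4 or more) cannot be computed by the stated rule.
- **PK.** Correctly timed Day 15 concentrations in both amcenestrant arms would be left out of the summary by time point.

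**Working it through.** The plan states no figure for these rules, so the check is to apply each one literally.

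**1. Stage: which rows can an eligible participant occupy?** The '11' in the T column of the extracted table is read as T1, a likely extraction slip.

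- I02, "Patients with histological or cytological proven diagnosis of invasive breast adenocarcinoma": removes Tis, 1 row.
- I05, "A breast tumor size of at least 10 mm in greatest dimension measured by ultrasound": removes T0, 2 rows.
- I03, "Stage I, Stage II or operable Stage III (excludes T4"): removes T4, 3 rows.
- E03 excludes "Evidence of metastatic spread by standard assessment according to local practice": removes M1, 1 row.

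Rows left: 18 − 1 − 2 − 3 − 1 = 11, namely T1 with N0, N1mi, N1, N2; T2 with N0, N1, N2; T3 with N0, N1, N2; and any T with N3. It is 10 if N3 disease is not counted as operable.

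Applying the note, all 11 are M0, so all 11 trip the distant-metastasis box, and 3 (T1N0, T2N0, T3N0) also trip the nodal box. Rows that return a stage: 0 of 11. Leaving the M0 box unchecked does not help, because no M0 row then matches. Over the whole table, 17 of 18 rows become not evaluable; the survivor is M1, which E03 excludes.

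**2. Reach of the stage error.** Table 4 lists age, race, tumor stage, tumor size, baseline Ki67, ER H-score and progesterone receptor: 7 factors. It does not say whether tumor stage means the Appendix A stage or the T category. If it means the former:

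- not evaluable kept as a category: stage is constant and 1 of 7 candidates is lost in each of 2 stepwise models;
- not evaluable treated as missing: a complete-case fit that includes stage could have no usable records.

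The SAP does not say which applies.

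**3. PEPI.** Integer H-scores from 0 to 300: 301 values. The bands 0-2 and 3-8 cover 0 to 8, which is 9 values. 9/301 = 3.0% covered; 301 − 9 = 292 have no points. On the 0-8 Allred scale all 9 values are scored. The item is worth 0 or 3 points, so it settles the risk category whenever the other items sum to 0-3:

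| Sum of other items | Total if ER item = 0 | Total if ER item = 3 |
|---|---|---|
| 0 | 0 (low) | 3 (medium) |
| 1 | 1 (medium) | 4 (high) |
| 3 | 3 (medium) | 6 (high) |

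If undefined totals are treated as missing, SAP 2.5.3 takes them out of the denominator. The percentages would then describe only participants with a post-treatment H-score of 0-8.

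**4. PK.** The schedule has Day 14 pre-dose, Day 14 at 3 h, and Day 15 at 24 h. 24 is not in [2, 4]. The pre-dose window does not apply either, since no dose is planned on Day 15. So 1 of 3 time points falls outside every window. Ceiling at planned size: 2 arms × 42 = 84 of 84 × 3 = 252 samples.

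**5. Primary analysis.** The ANCOVA in SAP 2.4.5.1.1 and Appendix D contains treatment and log baseline Ki67 only. mITT membership needs one dose and paired Ki67 values. None of the three derived variables enters.

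**The case against.** The best counter-argument is that these are visible drafting slips. The Appendix A table itself stages M0 rows, and a first run with every participant not evaluable would expose the error. The T, N and M items stay in the CRF, so nothing is lost. For PEPI, the protocol clearly specifies Allred and every other row of Appendix C agrees with it. For PK, the window sentence ends on a semicolon, so a clause may have dropped out in drafting or extraction. Day 15 values are still listed, and neither the PK/PD plots nor the concentration-ECG model depends on this window. The Table 4 consequences are conditional, and the CRF is not available to check.

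Much of this limits the consequence, and that part stands. It does not rescue the rules. A programmer who silently corrects Appendix A produces an output that departs from the SAP. The SAP's own change table records no move from Allred to H-score, and an Allred score has to be supplied by the laboratory, which programming cannot do. On the PK sentence, if Day 15 is read apart from the 2-4 h clause it has no window at all. Either reading leaves the 24 h sample uncovered in the text as it stands.

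**Conclusion.** The concern holds for all three rules. Stage: 0 of 11 reachable rows return a stage, so no eligible participant is staged. PEPI: 292 of 301 integer H-scores are unscored. That counts scale values; the share of participants is not given, and no misclassification is shown, only a gap. PK: 1 of 3 time points in 2 of 3 arms, at most 84 samples.

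The true PK number is below 84 because SAP 2.4 says the planned size will not be reached. It falls further if participants were enrolled before Amendment 02 (approved 26-Jan-2021), which introduced Day 15 sampling. As an assumption not found in the documents, 25%, 50% or 75% of 84 would be 21, 42 or 63 samples.

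The effect on subgroup, interaction and stepwise models depends on Table 4 using the Appendix A stage. The primary mITT Ki67 ANCOVA is unaffected, and PEPI and PK are exploratory. This should be fixed; its weight is low to moderate, and the stage rule matters most.

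**What to change.** Before database lock:

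- **SAP Appendix A.** Remove the N0 and M0 boxes from the not-evaluable list. Replace them with the CRF items recording that nodes or metastasis could not be assessed. That this was the intent is an inference, so check the wording against the CRF. State whether tumor stage in Table 4 is this anatomic stage or the T category.
- **SAP Appendix C.** Restore the Allred score from the central ER reading, as in protocol 8.1.3 and Table 16. State how a PEPI total with a missing item is handled.
- **SAP 2.4.7.1.** Add a Day 15 window around 24 h after the Day 14 dose, with its width set by the PK team. State how any Day 1 or Day 7 samples taken before Amendment 02 are summarised: Day 1 has no window and Day 7 only a pre-dose one.

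The cost is three text corrections, a check against the CRF, and an Allred score (or the data to derive it) from ER slides the central laboratory already reads. No new visits or samples are needed.
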